# 8. Data Quality Control and Database Management:

We will make every effort to minimize data recording errors by checking for outliers or abnormal values using frequency tables or graphical tools such as box plots. If noted, we will correct or check the validity of those values and discuss with practices. Although we expect few by virtue of randomization, we will examine imbalances between groups with respect to baseline practice demographic characteristics and outcome measurements. We will use standard statistical methods such as chi-square, Fisher exact, two sample t-tests or Mann-Whitney tests, depending on the outcome scale and validity of normal distribution assumptions. If necessary, we will apply log-transformations for right-skewed data. We will include variables that are significantly different in the above statistical models to control for their potential confounding effects. Although we anticipate little missing data based on prior QICs, when noted, we will examine reasons for incomplete records. We will analyze available data as the primary analytic strategy since mixed-effects modeling is valid for missing at random data. We will also conduct sensitivity analyses applying a full conditional specification multiple imputation method which can apply to missing not at random data. We will compare results between available data analysis and multiple imputations data analysis.

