# Methods:

This proposal aims to identify systems solutions for reducing harmful pediatric diagnostic errors. We will perform a prospective, stepped wedge cluster randomized controlled trial to test the hypothesis that QIC strategies can reduce three specific diagnostic errors in a national group of ambulatory pediatric primary care practices. These data will inform future diagnostic errors. Baseline data from the QIC will identify incidence data for errors in 3 separate stages of the diagnostic process: symptoms (missed diagnosis of adolescent depression), signs (missed diagnosis of pediatric elevated blood pressure) and diagnostic tests (delayed diagnosis of actionable laboratory results). Each of these diagnostic errors represents missed opportunities to recognize abnormal diagnostic findings. Human subjects' protection will be completed at the CHAM to cover the researchers and data analysis and at the American Academy of Pediatrics to cover all practices, as completed for prior QuIIN projects.

The goal of this proposal is to reduce diagnostic errors by tracking diagnostic errors rates (outcomes measures) and reliably performing best practices for diagnosing adolescent depression, pediatric elevated blood pressure and actionable laboratory results (process measures). In order to reduce overall data collection burden on practices and to increase engagement of practices that would have been in the control group, we have changed the study design. These changes do not affect the statistical power of the study. The intervention will consist of implementing QIC methodology in all practices to assist teams in reliably performing the processes that will reduce the diagnostic error outcomes via evidence-based tools. Practices will be randomized into three groups, with each group intervening on 1 diagnostic error and serving as the control group for a second diagnostic error. After 8 months of participation, each group will begin intervening on the diagnostic error they were a control group for, continue intervening on their original diagnostic error, and function as the control group for the third diagnostic errors. In the final 8 months of the QIC, all three groups will intervene on all three diagnostic errors.

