All practices will participate in the QIC for the full 2 years of the study. They will attend an initial 2-day interactive webinar learning session where they will learn QI methodology. enhance and practice QI skills, identify local 30-60 day aims for the diagnostic error they are intervening on first, increase their understanding of diagnostic errors and these errors in particular, and create systems for standardized data collection and data entry. Practices will submit monthly data on their intervention and control diagnostic errors but only receive centralized data feedback, coaching or collaborative involvement regarding their intervention error. (Figure 1) We acknowledge that error measurement in the baseline and intervention periods may introduce an intervention effect, but we have no reason to believe this effect will be different for the intervention and control practices. As noted above, after 8 months, practices will participate in a second 2-day video conference learning session, continue to intervene on their first error, begin to intervene on the error they were a control group for and begin to collect control data for the third diagnostic error. Including the control group in the QIC ensures that harm is prevented in the maximum number of patients and that clinical equipoise is met, as we believe this intervention will reduce errors. This stepped wedge design with two steps allows for the primary outcome comparison (diagnostic errors in intervention versus control) and secondary outcome comparisons: 1) diagnostic error rates in second wave participants), 2) Sustainability after first eight months and 3) collaborative effect for second wave practices. These secondary outcome comparisons will shed light on the effectiveness and sustainability of QICs and inform future collaborative designs.

Given concerns about practice attrition, we will additionally recruit a second wave of practices to join the collaborative. The three phase quality improvement research model lends itself to simply on-boarding a new group of practices and integrating them into the project in Phase 2 which would begin in June of 2016. The up to 15 Wave 2 practices would be recruited

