in the winter of 2015-2016, similarly randomized to the three already established collaborative groups and enrolled in March of 2016, collect baseline data comparable to the wave 1 practices and then participate in the collaborative beginning in June of 2016. As noted above, after 8 months, practices will participate in a second 2-day video conference learning session, continue to intervene on their first error, begin to intervene on the error they were a control group for and begin to collect control data for the third diagnostic error. The only difference between the Wave 1 and Wave 2 practices, are that the Wave 1 practices will ultimately intervene on all three diagnostic errors of interest. As the Wave 2 practices are entering the collaborative 8 months later, they will only intervene on two of the three diagnostic errors of interest over the course of 16 months. At the end of the collaborative, all resources and tools for the third diagnostic error will be given to the Wave 2 participants.

Target Diagnostic Error Outcome Measures:

All outcome metrics are described in detail in Table 2 and the Data Collection section below.

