## 4. Study Population

Our cohort will consist of at least 30 primary care pediatric practices which are part of QuIIN. We are confident that we can obtain this minimum number given that 45 of the 51 QuIIN practices (88%) participating in the pre-survey were interested in participating in a diagnostic error project, and over 300 practices are part of QuIIN from 46 states. We were able to recruit and consent 34 practices, but 9 were lost after randomization due to multiple issues including change in clinic staffing, change in clinic leadership and difficulty with data collection. For this reason we will recruit 15 additional practices to join the collaborative in Wave 2. Interested practices reported seeing between 3,000 and 80,000 pediatric patients per practice annually (median 12,000). No practices will be excluded based on size as even the smallest practices have sufficient patient panels to collect the data described above. Each practice-based team will be multidisciplinary, consisting of at least one physician, nurse and office practice associate allowing for microsystem issues to be transmitted to practice leadership and QI skill to be disseminated across key groups.

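### The only sensitivity analysis for missing data is credited with covering data missing not at random, but no term that would make it do so is specified, and 9 of 34 consented practices were lost after randomization

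*Combined protocol and SAP*

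**What the plan says.** Section 8 (Data Quality Control and Database Management) sets the primary approach: "We will analyze available data as the primary analytic strategy since mixed-effects modeling is valid for missing at random data". It adds one sensitivity analysis, "applying a full conditional specification multiple imputation method which can apply to missing not at random data", and states its use: "We will compare results between available data analysis and multiple imputations data analysis". It gives no imputation model, shift parameter or range, pattern-mixture or selection model, or reference-based rule. It does not say whether the unsubmitted months of a lost practice are imputed. It expects little missing data, on the strength of earlier collaboratives.

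Section 4 (Study Population) reports that 34 practices were recruited and consented, and that "9 were lost after randomization due to multiple issues including change in clinic staffing, change in clinic leadership and difficulty with data collection". The response is replacement: "For this reason we will recruit 15 additional practices to join the collaborative in Wave 2". Section 5 (Informed Consent) counts 30 Wave 1 practices, of which 25 were retained.

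**The concern.** FCS imputation (chained equations) draws each missing value from a conditional model fitted to the observed data. Unless the draws are shifted or the model is tied to the missingness pattern, it assumes that, given the modelled variables, missing outcomes behave like observed ones. That is MAR, the assumption on which the primary mixed model already rests.

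The planned comparison will nevertheless be read as a check on MNAR, because the plan says the method can apply there. Two MAR analyses can agree when loss depends on unobserved error rates. They can disagree for unrelated reasons, for example if the imputation ignores clustering. Neither result bears on MNAR. At stake is the only robustness statement the trial could make about the loss of whole randomized practices, a loss the document already reports.

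**Working it through.** **1. Practice loss.** Inputs: 34 consented and 9 lost (section 4, Study Population); 30 Wave 1 practices and 25 retained (section 5).
- 34 − 9 = 25, which reproduces the 25 retained.
- 9/34 = 26.5%, if all 34 were randomized.
- (30 − 25)/30 = 5/30 = 16.7% on the section 5 base.

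The document does not reconcile the two denominators, so both are carried forward.

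**2. Timing.** Wave 2 practices are added by "integrating them into the project in Phase 2 which would begin in June of 2016", and "As the Wave 2 practices are entering the collaborative 8 months later". Wave 1 therefore began about October 2015. The losses are reported as past while Wave 2 recruitment is still to come, and that recruitment is set for winter 2015-2016 with enrolment in March 2016. The losses therefore fall before about month 5.

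**3. Share of scheduled practice-months lost, per error.** In the first 8 months the practices are in three groups, "with each group intervening on 1 diagnostic error and serving as the control group for a second diagnostic error", so two of the three groups collect any given error. After month 8 all three do. Assumptions: equal thirds, losses spread evenly over groups, and exit somewhere between the start and month 5. Exit at month 5 loses 3 Phase 1 months in two-thirds of the lost practices, plus every later month.

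| Base | Window | Scheduled practice-months | Lost, exit at month 5 | Lost, exit at start |
|---|---|---|---|---|
| 34 (9 lost) | 12 months | 8 × 22.67 + 4 × 34 = 317.3 | 3 × 6 + 4 × 9 = 54 (17.0%) | 8 × 6 + 4 × 9 = 84 (26.5%) |
| 34 (9 lost) | 24 months | 8 × 22.67 + 16 × 34 = 725.3 | 3 × 6 + 16 × 9 = 162 (22.3%) | 8 × 6 + 16 × 9 = 192 (26.5%) |
| 30 (5 lost) | 12 months | 8 × 20 + 4 × 30 = 280 | 3 × 3.33 + 4 × 5 = 30 (10.7%) | 8 × 3.33 + 4 × 5 = 46.7 (16.7%) |
| 30 (5 lost) | 24 months | 8 × 20 + 16 × 30 = 640 | 3 × 3.33 + 16 × 5 = 90 (14.1%) | 8 × 3.33 + 16 × 5 = 106.7 (16.7%) |

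The 12-month rows match the first study year, which Statistical Models (section 7) names for the primary tests. The document does not give the losses by group, and uneven losses widen the range. With 9 of 34 lost, over 12 months, all 9 in the two collecting groups from the start gives 12 × 9/317.3 = 34.0%. All 9 in the group not collecting that error in Phase 1 gives 4 × 9/317.3 = 11.3%.

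**4. Can the planned comparison detect outcome-related loss?** A simulation illustrates the mechanism on assumed inputs. It does not model this trial's stepped design. It used two arms of 17 practices, 80 charts each and a generating log-odds effect of −0.5. Loss in the intervention arm depended on the practice's own follow-up rate, and on average 22.7% of practices were lost. Mean estimated log-odds effects were:
- all data: −0.473
- available data: −0.567
- imputation with no MNAR term: −0.565
- imputation with lost intervention practices shifted by +0.5: −0.458
- imputation with the shift at +1.0: −0.349

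Imputation without an MNAR term reproduced the available-data answer to within 0.002 while both were about 0.09 from the full-data answer. Only an explicit shift moved it. The direction and size here follow from the assumed dropout model and predict nothing about this trial.

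**The case against.** **The plan names MNAR as its target and leaves the mechanism open.** The sponsor could implement the imputation with a shift, so reading the silence as MAR is an inference about implementation. This stands in part: what is established is that no MNAR term is specified. But the plan attributes to the named method a property that it has only with such a term, so an analyst who follows the text would run a MAR imputation.

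**Other safeguards exist.** Section 8 also commits to examining reasons for incomplete records and to adjusting for baseline imbalances. Statistical Models lists baseline error rates and staffing among the covariates. These may make MAR more plausible, but none of them tests it. How far baseline outcomes could inform an imputation is itself unclear: Methods has each practice submit baseline data on one error, while Table 3 lists baseline charts for all three.

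**Wave 2 restores numbers.** It does, but it does not supply the outcomes of the lost practices.

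**Bias is not shown.** This stands in full. A reader might infer that losing whole randomized practices has biased the comparison. The documents do not support that. Staffing and leadership changes are not obviously outcome-related, each practice is in the intervention for one error and a control for another, and the losses are not given by group. Difficulty with data collection makes a link to error rates plausible, no more.

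A reader might also set an assumed shift against the 12-point detectable effects in Power Analysis. That would mix bases. Twelve points paired with a 13% reduction implies a base of 12/0.13 = 92%, whereas section 1 gives 74-87% missed for blood pressure and at most 26% delayed for laboratory results. The documents offer no source for the size of a shift.

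**Conclusion.** The concern holds as a fault in the missing-data plan: the sole sensitivity analysis is described as able to cover MNAR, no component that would make it do so is stated, and the planned comparison cannot inform on MNAR. The primary available-data model is not itself in question, and what lost practices did submit appears to be kept.

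The exposure is 26.5% of Wave 1 practices on a base of 34, or 16.7% on a base of 30. With losses spread evenly and exit before about month 5, this is 17.0% to 26.5% of scheduled practice-months per error in the first year on the base of 34, and 10.7% to 16.7% on the base of 30. These figures measure missing data, not bias, whose size and direction cannot be derived from the documents. The point should be addressed before analysis.

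**What to change.** 1. Describe the FCS imputation as a MAR analysis, and have it respect clustering by practice.
2. Add a pre-stated delta-adjusted (pattern-mixture) or tipping-point analysis for each of the three outcomes. Apply it to the months in which a lost practice was scheduled to collect that error. Let the shifts differ by intervention and control status, and run them in both directions over a range fixed in advance; a log-odds grid from −1 to +1, extended to the tipping point, is one option.
3. State that for depression a lower value is the unfavourable direction, because the variable counts diagnoses, whereas the other two outcomes count errors.
4. As clarifications, reconcile the 34 and 30 Wave 1 counts, and report practice loss by group and month of exit.

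The cost is SAP wording and additional multilevel imputation runs for three outcomes. No new data are needed. A narrower repair, relabelling the FCS analysis as MAR and nothing else, would correct the description but leave the trial with no analysis of outcome-related loss.
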